7.4.2 Unanticipated Problems Involving Risks to Subjects or Other (UPIRSOs)

The phrase "unanticipated problems involving risks to subjects or others" is found, but not defined in the HHS regulations at 45 CFR 46, and the FDA regulations at 21 CFR 56.108(b)(1) and 21 CFR 312.66. For device studies, part 812 uses the term unanticipated adverse device effect, which is defined in 21 CFR 812.3(s). Guidance from

the regulatory agencies considers unanticipated problems to include any incident, experience, or outcome that meets ALL three (3) of the following criteria:

- Unexpected in terms of nature, severity or frequency given (a) the research procedures that are described in the protocol-related documents, such as the IRB-approved research protocol and informed consent document; and (b) the characteristics of the subject population being studied;
AND
- Related or possibly related to participation in the research (possibly related means there is a reasonable possibility that the incident, experience, or outcome may have been caused by the procedures involved in the research);
AND
- Suggests that the research places subjects or others at greater risk of harm (including physical, psychological, economic, or social harm) than was previously known or recognized. Note: According to OHRP, if the adverse event is serious, it would always suggest a greater risk of harm.

Follow-up

All adverse events will be followed up according to good medical practices.

7.5 Reporting SAEs and UPIRSOs to the Simmon's Cancer Center (SCCC) Data Safety Monitoring Committee (DSMC)

All SAE/UPIRSOs at all sites, which occur in research subjects on protocols for which the SCCC is the DSMC of record require reporting to the DSMC regardless of whether IRB reporting is required. All SAEs/UPIRSOs occurring during the protocol-specified monitoring period should be submitted to the SCCC DSMC within 5 business days of the PI or delegated study team members awareness of the event(s). In addition, for participating centers other than UTSW, local IRB guidance should be followed for local reporting of serious adverse events.

UTSW reportable event guidance applies to all research conducted by or on behalf of UT Southwestern, its affiliates, and investigators, sites, or institutions relying on the UT Southwestern IRB. Additional reporting requirements apply for research relying on a non-UT Southwestern IRB.

According to UTSW HRPP/IRB policy, UPIRSOs are incidents, experiences, outcomes, etc. that meet **ALL three (3)** of the following criteria:

1. Unexpected in nature, frequency, or severity (i.e., generally not expected in a subject's underlying condition or not expected as a risk of the study; therefore, not included in the investigator's brochure, protocol, or informed consent document), AND
2. Probably or definitely related to participation in the research, AND
3. Suggests that the research places subjects or others at a greater risk of harm (including physical, psychological, economic, or social harm) than was previously known or recognized. Note: According to OHRP, if the adverse event is serious, it would always suggest a greater risk of harm.

For purposes of this policy, UPIRSOs include unanticipated adverse device effects (UADEs) and death or serious injury related to a humanitarian use device (HUD).

UPIRSOs must be promptly reported to the UTSW IRB within 5 working days of PI awareness.

For research relying on a non-UT Southwestern IRB (external, central, or single IRB):

Investigators relying on an external IRB who are conducting research on behalf of UT Southwestern or its affiliates are responsible for submitting **LOCAL** UPIRSOs to the UT Southwestern IRB within 5 working days of PI awareness. Investigators must report to their relying IRB according to the relying IRB's policy. In addition, the external IRB's responses or determinations on these local events must be submitted to the UT Southwestern IRB within 10 working days of receipt.

Events NOT meeting UPIRSO criteria:

Events that do NOT meet UPIRSO criteria should be tracked, evaluated, summarized, and submitted to the UTSW HRPP/IRB at continuing review.

For more information on UTSW HRPP/IRB reportable event policy, see <https://www.utsouthwestern.edu/research/research-administration/irb/assets/policies-combined.pdf>.

For further guidance for Investigators regarding safety reporting requirements for INDs and BA/BE studies, refer to FDA Draft Guidance document: <http://www.fda.gov/downloads/Drugs/GuidanceComplianceRegulatoryInformation/Guidances/UCM227351.pdf>

7.6 Steps to Determine If an Adverse Event Requires Expedited Reporting

Step 1: Identify the type of adverse event using the NCI Common Terminology Criteria for Adverse Events (CTCAE v4).

Step 2: Grade the adverse event using the NCI CTCAE v4.

Step 3: Determine whether the adverse event is related to the protocol therapy Attribution categories are as follows:

- Definite – The AE *is clearly related* to the study treatment.
- Probable – The AE *is likely related* to the study treatment.
- Possible – The AE *may be related* to the study treatment.
- Unlikely-The AE may NOT be related to the study treatment.
- Unrelated – The AE *is clearly NOT related* to the study treatment.

Note: This includes all events that occur within 30 days of the last dose of protocol treatment. Any event that occurs more than 30 days after the last dose of treatment and is attributed (possibly, probably, or definitely) to the agent(s) must also be reported accordingly.

Step 4: Determine the prior experience of the adverse event.

Expected events are those that have been previously identified as resulting from administration of the agent. An adverse event is considered unexpected, for expedited reporting purposes only, when either the type of event or the severity of the event is not listed in:

- the current known adverse events listed in the Agent Information Section of this protocol;
- the drug package insert (if applicable);
- the current Investigator's Brochure (if applicable);
- the Study Agent(s)/Therapy(ies) Background and Associated Known Toxicities section of this protocol.

7.7 Reporting Requirements for Adverse Events

7.7.1 Expedited Reporting

- The Principal Investigator must be notified within 24 hours of learning of any serious adverse events, regardless of attribution, occurring during the study or within 30 days of the last administration of the study drug.
- If necessary, suspected adverse reactions will also be reported to FDA at [name] or www.fda.gov/medwatch.

- The IRB must be notified within 10 business days of “any unanticipated problems involving risk to subjects or others” (UPR/UPIRSO).

The following events meet the definition of UPR:

1. Any serious event (injuries, side effects, deaths or other problems), which in the opinion of the Principal Investigator was unanticipated, involved risk to subjects or others, and was possibly related to the research procedures.
 2. Any serious accidental or unintentional change to the IRB-approved protocol that alters the level of risk.
 3. Any deviation from the protocol taken without prior IRB review to eliminate apparent immediate hazard to a research subject.
 4. Any new information (e.g., publication, safety monitoring report, and updated sponsor safety report), interim result or other finding that indicates an unexpected change to the risk/benefit ratio for the research.
 5. Any breach in confidentiality that may involve risk to the subject or others.
 6. Any complaint of a subject that indicates an unanticipated risk or that cannot be resolved by the Principal Investigator.
- The FDA should be notified within 7 business days of any unexpected fatal or life-threatening adverse event with possible relationship to study drug, and 15 business days of any event that is considered: 1) serious, 2) unexpected, and 3) at least possibly related to study participation.

7.7.2 Routine Reporting

- All other adverse events- such as those that are expected, or are unlikely or definitely not related to the study participation- are to be reported annually as part of regular data submission.

7.8 Stopping Rules

The study will be stopped if the combination treatment of SAbR and Nivolumab resulted in >50% of increased Grade 3-5 toxicity as compared to those reported in the literature for patients receiving Nivolumab alone in the first 6 patients assigned to the experimental arm and the regimen is deemed to be unsafe by the Data Safety Monitoring Committee.

8.0 DRUG INFORMATION

8.1 Nivolumab

- Other names for the drug(s): Opdivo
- Classification - type of agent: Monoclonal antibody, Antineoplastic Agent, Immunotherapy, PD-1 inhibitor, Miscellaneous; Biological Response Modulator
- Mode of action: Immune-stimulator; Binds to PD-1 receptor on immune cells and prevents the interaction of PD-1 with PD-L1 on cancer cells. By inhibiting this interaction (which inhibits the immune response), Nivolumab is thought to activate the immune response in a non-specific manner
- Storage and stability: Nivolumab vials must be stored at a temperature of 2°C to 8°C and should be protected from light. If stored in a glass front refrigerator, vials should

be stored in the carton. Care must be taken to assure sterility of the prepared solution as the product does not contain any anti-microbial preservative or bacteriostatic agent. No incompatibilities between Nivolumab and polyvinyl chloride (PVC), non-PVC/non-DEHP (di(2-ethylhexyl)phthalate) IV components, or glass bottles have been observed.

- Protocol dose: Per standard of care approved guidelines.
- Preparation: BMS-936558 (Nivolumab) 100 mg (10 mg/mL) will be packaged in an open-label fashion. Ten BMS-936558 10 mL vials will be packaged within a carton.

Route of administration for this study: Nivolumab administered per standard of care according to institutional guidelines. The standard FDA approved administration and indications of Nivolumab is listed in the FDA website: www.fda.gov or Package Insert https://www.accessdata.fda.gov/drugsatfda_docs/label/2018/125554s058lbl.pdf.

- Incompatibility: None
- Availability: Commercially available from Bristol-Myers Squibb.
- Side effects: See 7.2.4
- Nursing implications: As dictated by clinical course
- Nivolumab may be administered in a community practice setting as long as the treating study oncologist assumes responsibility for all reporting and follow-up requirements.

9.0 CORRELATIVES/SPECIAL STUDIES

The goal of the planned laboratory correlative studies is to measure the induced immune response to patient's pre-treatment tumor tissue antigens (see section 1.5 for detail). In addition, the correlative studies will evaluate the immune response generated by the regimen. The submission of collected whole blood is mandatory and will be performed at baseline, follow up q 8-12 weeks (until discontinued or within first year of enrollment, whichever is first) and at 1 year (if discontinued before 1 year).

9.1 Sample Collection Guidelines

Samples will be labeled with the subject's de-identified study number and collection date and delivered for analysis during regular business hours to: NC7: 208; Attn [name]

9.1.1 Whole blood sample: Patient's whole blood will be collected in EDTA (Lavender top) tubes for ~ 40-50 ml. In addition, ~10 ml will be collected in anti-coagulant-free tubes (Red top) for the collection of sera. The blood will immediately be processed (within 2 hours) by centrifugation (1000 g, 15 min, 4°C), collecting the supernatant and freezing at -80°C in 5 aliquots for future experiments. The pellet will be re-suspended in PBS and PBMC will be isolated using standard protocol. Briefly, the cell suspension will be carefully placed on 10ml polystyrene tube containing 1ml ficoll and centrifuged (400g, 30min, RT). PBMC region will be collected from the ficoll and washed 3x with PBS. Cells will be counted and frozen in 5 aliquots with 10% DMSO, 90% FBS at -80°C.

9.1.2 Tumor Biopsy Sample: A CT-guided biopsy of tumor lesion consisting of 4-5 18G needle cores is recommended at the time of registration of the patients to

the study unless a biopsy has been done in the previous 12 months (See 5.1.15). A second biopsy at 8 weeks (+/- 2 week) is elective.

9.1.2.1

Initial required biopsy: 3-4 core biopsies will be processed as routine diagnostic specimens by Pathology for the purpose of diagnosis and immuno-histochemistry (IHC). After on site adequacy check using touch imprint slides, the cores will be fixed in 10% buffered formalin for up to 8 hours and processed routinely to obtain formalin fixed paraffin embedded blocks. Eight, 3-micron thick sections will be cut. The first and last sections will be stained with hematoxylin and eosin (H&E) stain to evaluate the presence, extent, and grade of renal carcinoma. The remaining sections will be used to perform immunohistochemical staining if needed (see section 9.2 for IHC detail). **Two additional cores** will be placed in normal saline on wet ice and brought to NC9.208 ([name]) for generation of tumor lysates to be used as a source of antigen in the immunoassays. The biopsy cores will be chopped into minute pieces. Small volume of normal saline is added and the mixture is passed through a 19G needle, attached to a 5 ml syringe, several times, until the passage of the mixture occurred without difficulty. The process is repeated with 21G, 23G, and if possible 25G needle. The entire mixture is placed in liquid nitrogen until frozen, and then thawed in a water bath at 42°C. The freezing and thawing is repeated for a total of five times. The sample is passed through another 23G or 25G needle to disperse any clumps. The sample is then centrifuged at high speed, the supernatant collected, protein concentration measured using NanoDrop2000 and frozen at -80 °C in 5 aliquots.

9.1.2.2

8 week Elective Biopsy: One core from the biopsy will be processed by pathology to generate slides for histology and IHC. The second and third core will be placed in normal saline on wet ice and brought to NC9.208 ([name]) for processing for flow cytometry of cells. The tumor tissue is first cut into small pieces and incubated in PBS containing DNase I 1mg/ml (Roche Diagnostics, Indianapolis, IN) and Collagenase 2mg/ml (Fisher Scientific, Pittsburgh, PA) for 1h at 37°C. The lysate is then passed through cell strainer in PBS and washed 2x in 10ml of PBS followed by RBC lysis buffer. The cells are then frozen in 4 aliquots with 10%DMSO 90%FBS in -80°C for future flow cytometry analysis.

9.2 Assay Methodology

9.2.1 Elispot: IFN- γ ELISpot assays will be performed according to manufacturer's protocol using a commercial ELISpot kit (MabTECH). Briefly, 96 well plates are coated overnight with 0.015 mg/ml of an anti-human IFN- γ monoclonal antibody. PBMC from patients will be incubated in triplicates wells and stimulated in the presence of either PA2024 (10 μ g/ml), protein lysate from patient biopsy (50 μ g/ml) or 5 ng/ml PMA and 0.5 ng/ml ionomycin as positive control and albumin as negative control. For ELISPOT assays, plates are incubated for 48 hours, washed, probed with biotinylated anti-IFN γ , further washed, and then incubated with streptavidin alkaline phosphatase. Spot development is achieved with 5-bromo-4-chloro-3-indolyl phosphate/nitroblue tetrazolium (BCIP/NBT; Invitrogen) and spots are enumerated by an automatic ELISpot reader.

9.2.2 ELISA: In this procedure, patient tumor tissue lysate is first adsorbed to an EIA 96 well microplate (Fischer). Patient plasma is then added to each well as a source

of primary antibody and serially diluted. After extensive washes, detection enzyme (HRP)-linked anti-human mAb is then added to each well and allowed to bind. Appropriate substrate is then added to each well and color development occurs within 5-60 min. UV Microplate Reader will be used to read the plates

- 9.2.3 ³H-thymidine Proliferation Assay:** PBMC from patients will be incubated in a similar manner as above for five days at 37 °C then overnight with 0.5 mCi tritiated ³H-thymidine, harvested onto a glass-fiber filter using a 96-well FilterMate cell harvester. The radioactivity of the ³H-thymidine is detected by a direct betaplate counter. The degree of antigen-specific clonal T cell expansion will be expressed as a stimulation index (SI) of the ratio of ³H-thymidine incorporation by cells incubated with patient tumor lysate compared with media controls. An alternate method utilizing FACS analysis with carboxy fluorescein diacetate succinimidyl ester (CFSE) is also available [107].
- 9.2.4 Chromium Release Cytotoxicity Assays:** For cell-mediated cytotoxicity analysis, A 50 µl sample of ⁵¹Cr-labeled target cells (Caki-2 and ACHIN human renal cancer cells) is mixed with 100µl of effector cells (patient PBMC) at various target to effector ratio (E:T ratios). After centrifugation at 100 X G, the cells are incubated for 2 hr at 37°C. The radioactivity of culture supernatant is measured using a gamma counter and percentage of cytotoxicity is calculated. For antibody-dependent cytotoxicity analysis this procedure will be performed with patient's plasma instead of PBMC and the percentage of cytotoxicity is calculated in similar manner. An alternate and non-radioactive labeling method utilizes GAPDH enzyme release from lysed cells called Bioluminescence Non-Radioactive Cytotoxicity Assay (aCella-TOX, T Cell Technology, INC) [108, 109].
- 9.2.5 Flow cytometric analysis (FACS):** For FACS analysis of cell-surface molecules, the cell samples are stained with fluorescent dye – conjugated monoclonal antibodies against the selected markers on ice followed by fixation with 4% paraformaldehyde. Data are acquired on a LSRII (BD Biosciences) and analyzed using FACSDiva software (BD Biosciences). The PBMC of each patient before and after treatment will be analyzed to identify the relative sub-population of CTLs, regulatory T-Cells, effector memory T cells, MDSCs, neutrophils and NK cells utilizing appropriate cell surface markers.
- 9.2.6 Immunohistochemical staining (IHC):** Standard immunohistochemistry staining procedure for will be performed using the Benchmark XT automated stainer (Ventana) for both antibodies. Briefly, formalin-fixed, paraffin-embedded tissue sections will be cut at 3-4 micron and air-dried overnight. The sections will be deparaffinized, rehydrated, and subjected to heat-induced epitope retrieval. Sections will then be incubated with appropriate primary antibody. For signal detection, ultraView universal detection system (Ventana) will be used. The slides will be developed using 3-3'-diaminobenzidine chromogen and counterstained with hematoxylin. Appropriate positive and negative controls will be utilized for each run of immunostains. The evaluation of the immunostaining will be carried out by a genitourinary pathologist without knowledge of any clinicopathologic data. Only nuclear reactivity will be considered positive. An H score will be assigned as the product of average intensity of staining (0 for negative, 1 for weakly positive, 2 for moderately positive, and 3 for strongly positive) and extent of immunoexpression (0-100% percentage of cells staining). In addition, Dual-antibody ISH will be performed to identify and analyze TILs, CTL (CD3+,CD8+), Tregs (CD4+FoxP3), DC (CD11c) , NK/T (CD3+, CD1d), neutrophils (CD11b, Ly6G} and MDSC (CD14+,CD11b) in the tumor tissue before and after treatment, when available. PD-L1 expression will be quantified from biopsies of tumors prior to treatment.

9.2.7 Serum Cytokine Analysis: Multiplex cytokine analysis in patient's plasma will be performed in precoated 96 well plates (Human TH1/TH2 10 plex ultrasensitive assay, Meso Scale Discovery – MSD, Maryland, USA) according to manufacturer's instructions. 25 µL of diluent 2 is dispersed into each well. The plate is sealed and incubated by vigorous horizontal shaking for 30 minutes at RT.

25 µL of the patient plasma is added per well and all samples measured in triplicates. Plates are sealed and incubated by vigorous horizontal shaking for two hours at RT. Plates are washed three times with 0.05% Tween 20 in PBS. 25 µL of 1× detection antibody solution is placed per well and sealed plates are incubated by vigorous horizontal shaking for two hours at RT. Plates are washed three times with 0.05% Tween 20 in PBS. 150 µL of 2× Read Buffer T is added to each well. Plates are analysed using the MSD SECTOR Imager 2400 and Discovery Workbench 3.0 software (both from Meso Scale Discovery, USA). The mean value of two wells is taken as the recorded reading, provided that the coefficient of variation (CV) was less than 10%. Concentrations recorded lower than the standard curve are kept as absolute values. For purposes of logarithmic analysis, readings of 0 are adjusted to 0.01 pg/ml. The following cytokines will be measured before and after treatment for each patients: Th1/Th2/Th17 cytokines, IFN-γ, IL-1β, IL-2, IL-4, IL-5, IL-8, IL-10, IL-12p70, IL-13, IL-17 TNF-α; pro-inflammatory cytokines: GM-CSF, IFN-γ, IL-1β, IL-2, IL-6, IL-8, IL-10, IL-12p70, TNF-α; Chemokines: Eotaxin, MIP-1β, TARC, IP-10, IL-8, MCP-1, MCP-4 and others including IL-6, TGF-β and HMGB1 (see section 1.5).

9.2.8 Western-blot/Immuno-blot: Caki-2 and ACHIN human renal cancer cells lysate will be used to perform immune-blott using plasma collected from patients before and after treatment. The Caki-2 and ACHIN cell 10⁶ cells/mL will be lysed in immunoprecipitation assay buffer on ice for 30 min. Standard western blott methodology will be utilized. Briefly, 400 µg of protein will be separated using pre-made gradient 4% to 12% Bis-Tris gels (Invitrogen, Burlington, ON, Canada) and transferred to nitrocellulose. Patient sera/plasma will be diluted 1/500 in Blotto (5% dry milk powder; 0.1% Tween 20; 50 mmol/L Tris; 150 mmol/L NaCl) and incubated with nitrocellulose membranes for 1 h at room temperature using a multichannel immublotting device (Mini Protean II Multiscreen, Bio-Rad, Mississauga, ON, Canada). The membrane will then incubated for 1 h at room temperature with horseradish peroxidase–conjugated goat anti-human IgG (H+L; Jackson ImmunoResearch, West Grove, PA) diluted 1/10,000 in Blotto and visualized by enhanced chemiluminescence.

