Enhancements of increased cytotoxicity to renal cancer cells can be measured by cytotoxicity assays. Antibody-dependent cell-mediated cytotoxicity (ADCC) measures the cell-killing ability of certain lymphocytes that require the target cell to be marked by an antibody and thus measures the humeral response [57]. On the other hand, lymphocyte-mediated cytotoxicity assay will measure the formation of tumor-specific CTLs among the lymphocytes collected from patients before and after SABR and Nivolumab. Since it is not practical or feasible to obtain sufficient quantities of tumor cells from each patient to quantitatively assess cytotoxicity by these assays, established allogenic human renal cancer cell line Caki-2 and ACHIN will be used for this purpose. It is a generally accepted principle of tumor immunology that there will be many common tumor antigens between different patient tumors of same site origin, and therefore tumor cell lines as well [57]. In fact, the tumor antigens (PSA, CEA, CA 19-9 etc.) that are in clinical practice are reported to be present in a significant portions of patients of the respective tumor site. This concept of commonality of tumor antigens between allogenic tumor cell lines and patients is put into clinical practice by the GVAX anti-tumor vaccine which is currently in early phase clinical trials for pancreatic, melanoma and renal cancer [58, 59]. GVAX consists of multiple human tumor cell lines of the respective site that is modified to express GM-CSF, and killed with radiation prior to injection in patients. The presence of common tumor antigens in the cell lines and patient's tumors, leads to induction of an immune response. The LNCaP and PC-3 cell lines has been shown to express many of the common renal cancer antigens, and therefore, is an appropriate surrogate to be used instead of patient's own cells and has been used in similar *in vitro* cytotoxicity assays [60-64].

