2.3 Exploratory Objectives

- 2.3.1 To measure treatment-related tumor-specific immune response (immunogenicity).
- 2.3.2 To explore the immunological biomarkers (PD-L1 expression in tumor, DC-HIL expression in MDSC, TCR diversity and clonality, etc) as correlates or predictors for treatment response.
- 2.3.3 To evaluate the cost-effectiveness and cost-utility of the addition of SABR to Nivolumab in patients with mRCC

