2.4 Endpoints

- 2.4.1 **Response:** Treatment response will be measured using both the RECIST and immune related RECIST criteria (ir-RECIST), a minor modification of RECIST 1.1 for immunotherapy [89]. Radiated lesions will be excluded from target lesions.
- 2.4.2 **Death:** Death due to any cause, although in mRCC patient population, the overwhelming majority is expected to be secondary to disease progression.
- 2.4.3 **Progression:** Progression will be defined according to the ir-RECIST criteria and verified by a second set of imaging at least 6 weeks apart.
- 2.4.4 **Immune Response:** Immune response will be measured using ELISpot assay, T-cell proliferation assay and ELISA.
- 2.4.5 **Toxicity:** Toxicity will be measured using CTAE v4.0

- 2.4.6 HR-QoL:** HR-QoL will be measured using FACT-G, EQ-5D and FKSI questionnaires at baseline, and at different time-points during treatment and follow up
- 2.4.7 Cost-effectiveness analysis:** Health care utilization data needed to assess costs will be obtained from patients' insurance claims during and after treatment. Markov modeling with probabilistic sensitivity analysis will be used to correlate quality-adjusted survival and cost.

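### Section 9.2.4 runs the antibody-dependent cytotoxicity assay on plasma without effector cells, which does not match the ADCC that section 1.5 describes

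*Combined protocol and SAP*

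**What the plan says.** Section 1.5 (Correlative Studies) announces two cytotoxicity assays. One is ADCC, which it says "measures the cell-killing ability of certain lymphocytes that require the target cell to be marked by an antibody", and which it treats as a reading of the humoral response. The other is a lymphocyte-mediated assay for tumor-specific CTLs. For the targets in both, "established allogenic human renal cancer cell line Caki-2 and ACHIN will be used for this purpose".

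Section 9.2.4 gives the method. For the cell-mediated version, labelled Caki-2 and ACHIN cells are mixed with patient PBMC as effectors at several effector-to-target ratios, incubated, and the radioactivity released into the supernatant is counted. For the antibody-dependent version, "this procedure will be performed with patient's plasma instead of PBMC", and the percentage of cytotoxicity is calculated in the same way.

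Section 9.1.1 describes the samples. Whole blood is centrifuged, "collecting the supernatant and freezing at -80°C in 5 aliquots for future experiments". PBMC are then isolated from the pellet and frozen separately, also in 5 aliquots.

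**The concern.** By section 1.5's own account, ADCC needs three things in the well: a target cell, an antibody bound to it, and a lymphocyte to do the killing. The method section substitutes plasma for the lymphocytes when it should presumably combine the two. A laboratory that followed section 9.2.4 to the letter would produce a percentage of cytotoxicity for each patient and time point. That figure could be tabulated as ADCC although the killing cell was never present.

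At stake is the one planned test of whether patient antibody can direct killing of renal cancer cells. The other antibody assays, ELISA (9.2.2) and immunoblot (9.2.8), show that antibody binds, not that it leads to killing.

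**Working it through.** The plan states no figure to reproduce. The check sets the definition beside the method and looks for a missing component.

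**1. Components required and components supplied**

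| Component | Section 1.5, ADCC | Section 9.2.4, cell-mediated | Section 9.2.4, antibody-dependent |
|---|---|---|---|
| Target cells | Caki-2, ACHIN | Caki-2, ACHIN | Caki-2, ACHIN (same procedure) |
| Patient antibody | required | not added | patient plasma |
| Effector lymphocytes | required | patient PBMC | removed |

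**2. Is there another source of effectors?** Section 9.1.1 takes plasma from the supernatant and PBMC from the pellet, so plasma is not a planned source of lymphocytes. Sections 9.0 to 9.2.8 mention no donor PBMC, NK cells or effector cell line for these wells. The non-radioactive alternative in 9.2.4 changes how lysis is detected, not what is in the well.

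**3. Are the two sections describing the same assay?** Section 1.5 lists one antibody-dependent and one lymphocyte-mediated cytotoxicity assay on Caki-2 and ACHIN. Section 9.2.4 lists one antibody-dependent and one cell-mediated assay on the same lines. Section 9.0 sends the reader to section 1.5 for detail. The pairing is clear, although 9.2.4 leaves the words for cell-mediated out of the name of the antibody-dependent version.

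**4. What the literal method can show.** Write the release in a well as

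total release = spontaneous + plasma-mediated + lymphocyte-mediated.

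With no lymphocytes added, the last term is absent, and it is the only term that section 1.5 calls ADCC. The effector-to-target ratios carried over from the cell-mediated version have nothing to refer to. Total release need not be zero.

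**5. How far this reaches.**
- The work serves an exploratory objective (2.3.1).
- For the immune-response endpoint, section 2.4.4 states: "Immune response will be measured using ELISpot assay, T-cell proliferation assay and ELISA". Neither cytotoxicity assay is on that list.
- Section 1.5 also assigns the humoral response to ELISA, and tumor-antigen-specific antibody to immunoblotting.
- Section 11.3 does not name the cytotoxicity results in any planned analysis.

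**6. Can banked baseline PBMC serve as the effector?** Four assays already draw on PBMC: ELISpot, proliferation, cell-mediated cytotoxicity and FACS. If each used one of the 5 baseline aliquots (an assumption; the protocol gives no cell yields or requirements), 5 − 4 = 1 would remain. A patient sampled every 8 to 12 weeks for a year has about 52/12 = 4.3 to 52/8 = 6.5 follow-up draws besides baseline. That single aliquot would have to serve all of those plasma samples on two target lines. The documents do not show whether it would suffice.

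**The case against.** The strongest reply is that section 9.2.4 is a summary and gives this variant one sentence. Three readings are open: plasma is the patient-derived variable and the effector source is simply unstated; a plasma-only lysis assay is intended and section 1.5 is worded wrongly; or the sentence is a slip for plasma in addition to PBMC. The laboratory may well add effectors in practice. This stands as a limit on the claim. It does not remove the conflict, because the sentence as written names a substitution, and under each reading at least one of the two sections needs to change.

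A reader might also infer that a flat result would be taken as evidence of no humoral response to SABR plus nivolumab. The documents do not support that. The humoral response is measured directly by ELISA and immunoblot, and the cytotoxicity assays are outside the immune-response endpoint, so a null result here would be read beside two antibody measurements. What remains is narrower: a flat result could be reported as absent antibody-directed killing when the assay could not have detected it.

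**Conclusion.** The point holds as an internal contradiction with a small reach. Followed literally, section 9.2.4 cannot deliver the ADCC read-out promised in section 1.5, for any patient or time point. This rests on one assumption: that no effector cells are added beyond what the protocol states. It would be too strong to say that the trial will certainly obtain no ADCC data, since the documents do not exclude an effector source that went unwritten.

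The effect is confined to one variant of one exploratory assay. The response-rate endpoint, the sample size, the safety hold after the first six patients and patient procedures are untouched. It is a minor correction, worth making because it is cheap.

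**What to change.** Make one of two edits, according to what was intended.

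- **If ADCC is intended:** in section 9.2.4, replace the substitution with patient plasma together with a fixed, named effector-cell source at a stated effector-to-target ratio, so that only the plasma changes over time. Add two control wells: plasma without effectors, to measure plasma-mediated lysis, and effectors without patient plasma. The second is needed because the same section uses PBMC alone to measure killing of these lines, so lysis with effectors present cannot otherwise be credited to antibody. Use each patient's baseline PBMC only if the 5 stored aliquots are shown to be enough after the other assays; otherwise choose another fixed source.
- **If a plasma-only lysis assay is intended:** reword section 1.5 to say what that assay measures, and do not report the result as ADCC.

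The first option costs some effector cells and a few extra wells per plate, and obtaining another effector source if baseline PBMC fall short. The second costs a change of wording and gives up the lymphocyte-mediated read-out. Neither needs an added patient visit or blood draw.
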